4 STUDY MEASUREMENTS AND VARIABLES

4.1 Endpoints

4.1.1 Primary Endpoint

Plasma RPL554 pharmacokinetic parameters (AUC_{0-24} , C_{max} , t_{max}).

4.1.2 Secondary Endpoints

Secondary endpoints are:

- Peak and AUC FEV₁ over 4, 6 and 8 hours
- Determination of onset of action
- Determination of duration of action
- Safety and tolerability
 - Continuous monitoring of adverse events
 - Laboratory safety tests (haematology, biochemistry and urinalysis)
 - 12-lead ECG (including QTcF and heart rate), supine vital signs (blood pressure and pulse) over 8 hours

4.1.3 Exploratory Endpoints

Levels of inflammatory mediators in sputum and sputum rheology.

4.2 Screening and Demographic Measurements

Written informed consent will be obtained by the Investigator prior to any study related procedures being performed.

Demographic variables, including date of birth, sex (plus details confirming non-childbearing status for females), height, weight, BMI (weight [kg]/height [m]²), race, ethnic origin and smoking status will be collected at screening (Visit 1). The date of diagnosis of CF and the specific CF mutations will also be recorded.

Active medical conditions and all surgeries will be recorded at screening (Visit 1), including disease history which includes date of diagnosis.

A reversibility test in response to salbutamol will be performed at screening (Visit 1). Spirometry (FEV₁ and FVC) will be performed before and after (at 30 minutes and 1 hour) two puffs of salbutamol administered using a pressurised metered dose inhaler. The pre-bronchodilator FEV₁ must be $\geq 40\%$ and $\leq 80\%$ of predicted normal for inclusion. The reversibility response is not an eligibility measure.

At all three time points, three technically acceptable measurements should be made and recorded in the CRF. Spirometry assessments may be repeated up to eight times to obtain three acceptable readings according to American Thoracic Society [ATS] guidelines (Miller, 2005). The highest reading from each assessment will be used for calculation of predicted values and increase from baseline. European Community of Coal and Steel reference equations (Quanjer, 1993) will be used as a reference for predicted normal values.

Laboratory safety assessments will be performed to check eligibility. Unscheduled and/or repeat testing may be performed at the discretion of the Investigator.

Prior respiratory therapies and medications will be recorded at screening (Visit 1) as well as concomitant use during the study. Other medications used prior or as concomitant use during the study will be recorded separately.

Patients will be confirmed as eligible according to the inclusion and exclusion criteria from assessments made at screening (Visit 1) with a final check of all results pre-dose at Visit 2.

4.3 Pharmacokinetic Measurements and Variables

Pharmacokinetic analysis will be performed on samples taken from all patients. Blood samples (4 mL) will be collected at the following time points at Visit 2 to Visit 4: pre-dose, 15 and 30 minutes and 1, 2, 4, 6, 8 and 24 hours post-dose. Samples will be collected by venepuncture or via indwelling cannula in the forearm into lithium heparin tubes and will be immediately chilled (ice bath). The blood will be centrifuged within 15 minutes of collection. The plasma will be separated in a refrigerated centrifuge (about 4°C) at 1100 g for 15 minutes and transferred into polypropylene tubes. After each blood collection, the plasma will be dispensed into two aliquots. After appropriate labelling, the plasma samples will be stored at, or below -20°C. The plasma samples will then be transported in dry ice to the central laboratory where they will be stored at or below -20°C until they are analysed using a validated method.

4.4 Pharmacodynamic Measurements and Variables

4.4.1 Spirometry

Spirometry assessments (FEV₁ and FVC) will be made at the following time points at Visit 2 to Visit 4: pre-dose (at -15 minutes) and 5, 15 and 30 minutes and 1, 2, 4, 6, 8 and 24 hours post-dose in accordance with ATS guidelines (Miller, 2005). At all time points, three technically acceptable measurements should be made and recorded in the CRF. Spirometry assessments may be repeated up to eight times to obtain three acceptable readings. The highest FEV₁ and FVC readings from each assessment will be used for analysis even if the FEV₁ and FVC values come from two different forced exhalations.

4.4.2 Sputum Inflammatory Mediators

Sputum samples will be taken pre-dose and at 8 and 24 hours post-dose at Visit 2 to Visit 4 by spontaneous expectoration over no more than 5 minutes and transported on ice for rapid processing (collection to storage within 30 minutes). Whole sputum will be immediately frozen at -20°C and then transferred to -80°C for storage prior to analysis (Horsley et al, 2014).

Rheological analysis will be performed before and after incubation at 37°C for 60 minutes (Horsley et al, 2014). Inflammatory mediators (IL-8, TNF- α and MPO) will be measured according to the published methodology (Downey et al, 2007).

4.4.3 Exhaled Breath pH

Exhaled breath pH will be measured pre-dose and at 8 and 24 hours post dose at Visit 2 to Visit 4. Exhaled breath pH measurement will be performed in accordance with the method described by MacNee et al, 2011. In brief, exhaled breath condensate (EBC) samples will be collected during tidal breathing for 10 minutes, without nose clips, using the RTube™ (Respiratory Research Inc., Charlottesville, Virginia). A 200 μ L aliquot of EBC will be used for the pH assay. Measurement of pH will be performed after deaeration by bubbling argon through the sample at 2 L/min while monitoring pH until the reading stabilised, usually after 8 minutes of deaeration with argon.

4.5 Safety Measurements and Variables

4.5.1 Adverse Events

Adverse event is defined as any undesirable experience occurring to a patient, or worsening in a patient, during a clinical study, whether or not considered related to the study treatment. An adverse event may be any of the following:

- A new illness
- An exacerbation of a sign or symptom of the underlying condition under treatment or of a concomitant illness
- Unrelated to participation in the clinical study or an effect of the study drug
- A combination of one or more of the above factors

No causal relationship with the study treatment is implied by the use of the term “adverse event.” An exacerbation of a pre-existing condition or illness is defined as a more frequent occurrence or as an increase in the severity of the pre-existing condition or illness during the study. Planned or elective surgical or invasive procedures for pre-existing conditions that have not worsened are not adverse events. However, any complication that occurs during a planned or elective surgery is an adverse event (if the event fits the serious criteria, such as an extended hospitalisation, it will be considered to be serious). Conditions leading to unplanned surgical procedures may be adverse events.

Adverse reaction is defined as all untoward and unintended responses to study treatment related to any dose administered.

Serious adverse event (SAE) is any adverse experience that:

- Results in death
- Is life-threatening
- Requires inpatient hospitalisation or prolongation of existing hospitalisation
- Results in persistent or significant disability/incapacity, OR
- Is a congenital anomaly/birth defect
- Other medical events*

*Important medical events that may not be immediately life-threatening or result in death or hospitalisation may be considered a SAE when, based on appropriate

medical judgement, they may jeopardise the patient or may require medical or surgical intervention to prevent one of the outcomes listed above.

An unexpected adverse reaction is an adverse reaction in which the nature or severity of which is not consistent with the Investigator Brochure.

Suspected unexpected serious adverse reactions (SUSAR) is any suspected adverse reaction related to the study drug that is both unexpected and serious.

All adverse events, whether reported spontaneously by the patient, in response to open questioning on treatment days or observed by the investigator or his/her staff, will be recorded from informed consent until the end of study visit (Visit 5). The start and stop time will be recorded and adverse events will be assessed by the investigator for the following:

- severity (mild, moderate, severe)
- chronicity (single occasion, intermittent, persistent)
- causality (not related, unlikely, possibly, definitely)
- action taken with study treatment (none, study treatment stopped, study treatment temporarily interrupted)
- other actions (none, concomitant medication, study discontinuation, hospitalisation, other)
- outcome and date of outcome (recovered or resolved, recovering or resolving, not recovered or not resolved, recovered or resolved with sequelae, fatal, unknown)
- seriousness (yes, no)

4.5.2 Laboratory Safety Measurements and Variables

All female patients will have a urine pregnancy test at screening (Visit 1), pre-dose at Visit 2 to Visit 4 and at the end of study visit (Visit 5) according to the study centre's standard operating procedures (SOPs).

All other laboratory safety assessments will be performed at the study centre's local laboratory. Two samples will be collected at each time point, one sample for haematology using a ethylenediaminetetraacetic acid (EDTA) whole blood collection tube and one sample for biochemistry using a serum tube. A midstream urine sample will also collected in a sterile container. Samples will be taken at screening (Visit 1) and end of study visit (Visit 5) and analysed for:

Haematology: haemoglobin, haematocrit, total white cell count, leukocyte differential count and platelet count

Biochemistry: creatinine, total bilirubin, alkaline phosphatase, aspartate aminotransferase, alanine transaminase, gamma-GT, lactate dehydrogenase, creatine kinase, thyroid stimulating hormone, triiodothyronine and thyroxine, glucose, potassium, sodium and calcium

Urinalysis: leukocytes, blood, ketones, bilirubin, urobilinogen, protein and glucose using a dipstick. In the event of an abnormal dipstick urinalysis result, microscopic urinalysis may be conducted. The referral criteria will be specified in the laboratory manual

In addition, unscheduled and/or repeat testing may be performed at the discretion of the Investigator. Laboratory results will be provided to the Investigator for each

patient and each visit. The Investigator should assign whether each abnormal result is not clinically significant or clinically significant.

4.5.3 Vital Signs

Blood pressure and pulse rate will be measured at screening (Visit 1) and pre-dose, 30 minutes and 1, 2, 4, 6 and 8 hours post-dose at Visit 2 to Visit 4

At each time point, supine vital signs will be assessed while the patient has been at rest for at least 5 minutes.

4.5.4 Physical Examination

A full physical examination, covering major body systems (assessments of the nose, throat, skin, thyroid gland, neurological system, respiratory system, cardiovascular system, abdomen [liver and spleen], lymph nodes and extremities) will be performed at screening (Visit 1). Results will be recorded in the CRF as normal, abnormal not clinically significant or abnormal clinically significant. The physical examination will be repeated at the end of study visit (Visit 5), and any changes only recorded.

4.5.5 12-Lead ECG

12-lead ECGs will be taken at screening (Visit 1) and pre-dose and 1, 2, 4 and 8 hours post-dose at Visit 2 to Visit 4.

At each time point, 12-lead ECGs should be taken after at least 5 minutes in the supine position. An ECG printout must be taken at each time point and signed and dated by the Investigator. An overall assessment (normal, abnormal not clinically significant or abnormal clinically significant) and continuous variables, including QT interval, QTcF and heart rate, will be recorded in the CRF.

5 DATA MANAGEMENT

Data management will be performed by Syne-qua-non. Data handling will be described in a Data Management Plan and a Data Validation Plan.

6 STATISTICAL METHODS AND DETERMINATION OF SAMPLE SIZE

6.1 Statistical Evaluation

The statistical analysis will be conducted by StatMind AB using SAS version 9.3 or higher. Validation will be performed using Gauss 6.25.

The statistical analyses and reporting of results (tables, figures and listings [TFL]) for this study follows the International Conference on Harmonisation (ICH) guidelines.

6.2 Description of Analysis Sets

Allocation of patients to the analysis populations (and whether any patients or specific data from a patient will be excluded) will be determined at the pre-database lock meeting.

The full analysis set [FAS] will consist of all randomised patients with sufficient data collected after intake of study treatment to compute the pharmacodynamic parameters on at least two study visits.

The completer analysis set [CAS] will consist of all randomised patients with sufficient data collected after intake of study treatment to compute the pharmacodynamic parameters on all three study visits.

The safety set will consist of all randomised patients with safety data collected after intake of study treatment during at least one visit.

The pharmacokinetic data set [PKS] will consist of all randomised patients with blood sampling performed after at least one dose of RPL554 and with data sufficient to calculate pharmacokinetic parameters.

6.3 Summary Statistics

Continuous variables will be summarised using descriptive statistics (number of patients [N], arithmetic mean, standard deviation [SD], median, minimum and maximum values) and for categorical (nominal) variables, the number and percentage of patients will be used. For continuous variables with an expected skew distribution (plasma RPL554 concentrations, some pharmacokinetic parameters [AUC₀₋₂₄, C_{max}], inflammatory cell mediators [IL-8, TNF- α , MPO]), geometric mean and coefficient of variation (CV) will be given instead of arithmetic mean and SD.

6.4 Methods of Statistical Analysis

6.4.1 Disposition

A summary of the patient flow (number and percentage) will be made of all patients enrolled in the study, randomized in the study, belonging to each of the analysis sets, completed the study or prematurely discontinued the investigational product.

The primary reason for withdrawal from the study will be summarized into the following categories: consent withdrawn, adverse event, protocol violation, investigator's decision, sponsor decision or other reason. Patient disposition data including individual reasons for withdrawal will be listed.

6.4.2 Demographic and Other Baseline Characteristics

Demographics and baseline characteristics including age, sex, race, ethnic origin, height, weight, BMI, smoking status, pack years, time since CF diagnosis, CF mutations, FEV₁ [both in litres and in percentage of predicted normal], FVC and FEV₁ reversibility will be listed and summarised by descriptive statistics.

Prior and concomitant CF therapies will be listed and summarised by ATC class for all enrolled patients (long-acting and short-acting LABAs and LAMAs will be separated).

Other medical history and other prior and concomitant medications will be listed. Medical history events will be coded using the MedDRA Dictionary in addition to the verbatim.

6.4.3 Extent of Exposure and Treatment Compliance

All administration of study treatment will be done at the clinic under supervision of the study staff; therefore no formal analysis of compliance will be performed. The

RPL554 exposure will be calculated based on residual volume in the nebuliser cup and summarised by treatment group. The exposure would equal (nominal volume – residual volume) times the drug concentration.

6.4.4 Protocol Deviations

Protocol deviations will be categorized as eligibility deviation, sample handling error, missed assessment, late or early assessment, outside visit window or other category. All protocol deviations collected will be divided into major or minor categories. Prior to database lock protocol deviations will be reviewed and consequences for inclusion of patients in various analysis population sets determined and documented. All details of protocol deviations in the study will be listed. Further protocol deviation will be summarised by category and minor/major assessment.

6.4.5 Pharmacokinetic Analysis

Blood sampling for pharmacokinetic assessments will be done pre-dose and up to 24 hours post-dose. From the plasma concentrations of RPL554 collected, the following pharmacokinetic parameters will be calculated using standard non-parametric methods.

- AUC_{0-24} is the area under the plasma concentration curve from time 0 to 24 hours post-dose, computed using the linear trapezoidal method
- C_{max} denotes the highest plasma concentration measured
- t_{max} denotes the time point corresponding to C_{max}

Pharmacokinetic parameters will be summarised by dose level using descriptive statistics. Graphics will include individual and mean plasma concentration – time curves (both on linear and semi-log scale) and scatter plots of computed pharmacokinetic parameters with mean levels indicated.

6.4.6 Pharmacodynamic Analysis

6.4.6.1 Spirometry

For FEV_1 the average effect, (E_{av}), will be calculated as the Area Under the Curve (AUC) divided by the length of the time interval of interest. The AUC will be computed using the linear trapezoidal rule. Linear interpolation/extrapolation will be used to fill in a missing value (at most one missing value allowed) at end of the computational interval prior to calculation. In addition, the peak effect on FEV_1 will be computed as the maximum value (E_{max}) within 4 hours post-dosing. In analysis, E_{av} and E_{max} will be normalized using the baseline value.

Computed pharmacodynamic parameters for FEV_1 will be compared between placebo and the two doses of RPL554 using analysis of covariance (ANCOVA) models with fixed factors for treatment, period and patient, and using the baseline of the day as a covariate. FEV_1 will be analysed using multiplicative models, which means that data is logged prior to analysis and the result then transformed back to the linear scale giving treatment differences as ratios of geometric means. All three pairwise comparisons will be stated and expressed as the geometric mean ratio with 95% confidence interval and associated, 2-sided, p-value.

All spirometry data will be listed and summarized by treatment and assessment point as well as the change from baseline. Pharmacodynamic parameters will be

summarized by treatment. Graphics will include individual and mean FEV₁ and FVC curves over time (expressed as change from baseline on absolute scale) and scatter plots of computed pharmacodynamic parameters with the mean levels indicated.

Onset of effect will be defined as time to reach a 10% increase in FEV₁ counted from start/end of nebulization. Patients not reaching a response after 2 hours will be censored. Outcome will be illustrated using a Kaplan-Meier plot and, if appropriate, the median time to onset by (active) treatment group determined.

Duration of effect will be assessed by consecutively testing effect of active treatment versus placebo for increasing time points using similar models as the analysis of the pharmacodynamics parameters. If missing values exist, these will be filled in using linear interpolation/extrapolation prior to analysis.

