6.2.1 Pre-Dose Assessments

- Confirm that respiratory medications were withheld as required. If not reschedule the visit for within the required window
- Questioning for adverse events
- Concomitant medication check
- Urine pregnancy test (female patients only)
- Nebuliser inhalation training
- 12-lead ECG
- Vital signs (blood pressure and pulse rate)

- Blood sample for pharmacokinetics
- Exhaled breath pH (UK centre only)
- Sputum for rheology and inflammatory mediator measurements
- Spirometry (one measurement at -15 minutes)

Eligible patients will then be randomised and receive a randomisation number.

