7.2 Pharmacodynamic Assessments

7.2.1 Pulmonary Function Tests

Spirometry assessments (FEV₁ and FVC) will be made at the following timepoints at Visit 2 to Visit 4: pre-dose (at -15 minutes), 15 and 30 minutes and 1, 2, 4, 6, 8 and 24 hours post-dose in accordance with ATS/European Respiratory Society (ERS) guidelines (Miller, 2005). At all timepoints, three technically acceptable measurements should be made and recorded in the CRF. Spirometry assessments may be repeated up to eight times to obtain three acceptable readings according to ATS guidelines (Miller, 2005). The highest FEV₁ and FVC readings from each assessment will be used for analysis even if the FEV₁ and FVC values come from two different forced exhalations.

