8.2 Graphs for Section 14.2-3

Safety set used for graphics if not otherwise indicated

- 14.2.1.1 Individual plasma concentration-time curves for RPL554 [PKS]
- 14.2.1.2 Mean plasma concentration-time curves for RPL554 [PKS]
- 14.2.1.3 Scatter plots of computed pharmacokinetic parameters [PKS]
- 14.2.2.1 Individual curves for FEV₁ on absolute scale [FAS]
- 14.2.2.2 Individual curves for FEV₁ as change from baseline [FAS]
- 14.2.2.3 Mean value curves for FEV₁ on absolute scale [FAS and CAS]
- 14.2.2.4 Mean value curves for FEV₁ as change from baseline [FAS and CAS]
- 14.2.2.5 Scatter plots of pharmacodynamic parameters based on FEV₁ [FAS]
- 14.2.2.6 Individual curves for FVC, absolute and as change from baseline [FAS]
- 14.2.2.7 Mean value curves for FVC, absolute and as change from baseline [FAS]
- 14.2.3.1 Individual curves for inflammatory mediators, exhaled breath pH and sputum rheology by treatment [FAS]
- 14.2.3.2 Mean value curves for inflammatory mediators, exhaled breath pH and sputum rheology, absolute and change from baseline [FAS]
- 14.3.4.1 Shift plots for laboratory data
- 14.3.5.1 Individual curves for vital signs, absolute and change from baseline
- 14.3.5.2 Mean value curves for vital signs, absolute and change from baseline
- 14.3.5.3 Individual curves for 12-lead ECG, absolute and change from baseline

- 14.3.5.4 Mean value curves for 12-lead ECG, absolute and change from baseline
- 14.3.5.5 Scatter plot of baseline QTcF versus post-dose assessment indicating largest absolute change from baseline

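### The onset-of-action summary has no placebo reference, so taken alone it cannot separate drug effect from chance 10% rises in FEV1

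*SAP*

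**What the plan says.** Onset is a listed secondary endpoint in Protocol 10.3.2 and SAP 4.1.2 ("Determination of onset of action"). The protocol does not define it. SAP 6.4.6.1 does: "Onset of effect will be defined as time to reach a 10% increase in FEV₁ counted from start/end of nebulization". On follow-up it adds: "Patients not reaching a response after 2 hours will be censored". The result goes on a Kaplan-Meier plot and, "if appropriate, the median time to onset by (active) treatment group determined".

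The reference for the 10% is not named. The only pre-dose spirometry timepoint is 15 minutes before dosing (Protocol 6.2.1: "Spirometry (one measurement at -15 minutes").

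The two documents differ on post-dose times. Protocol 7.2.1 has "15 and 30 minutes and 1, 2, 4, 6, 8 and 24 hours post-dose in accordance with ATS/European Respiratory Society (ERS) guidelines", which puts four readings inside 2 hours. SAP 4.4.1 has "and 5, 15 and 30 minutes and 1, 2, 4, 6, 8 and 24 hours post-dose in accordance with ATS guidelines", which puts five there.

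The other FEV1 endpoints in SAP 6.4.6.1 use placebo. Peak and average effect are compared with it by ANCOVA, and duration is tested against it at successive timepoints. SAP 8.1 lists a duration-of-action table (14.2.2.4). Neither SAP 8.1 nor 8.2 lists a table naming onset or a Kaplan-Meier figure.

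**The concern.** A profile counts as showing onset if any one of four or five readings reaches 10% above what is presumably a single pre-dose value. No second reading has to confirm it. One high reading, a low baseline, or an upward trend over the morning would each register as onset whatever was inhaled.

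The placebo period is what would show how often that happens. Protocol 3.2 justifies the crossover on the ground that patients serve as their own controls, and every completer has a placebo profile on the same schedule. The planned onset summary does not commit to using it. At stake is how a median time to onset, or the height of an active curve at 2 hours, would be read. Without the placebo figure beside it, some of what is shown may be background. With 10 completers, each chance crossing moves an arm's proportion by 10 percentage points.

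**Working it through.** The plan gives no error rate or variability figure for onset, so there is nothing to reproduce. The check asks how often a profile with no drug effect would meet the definition.

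**Inputs from the documents.** Threshold 10%; window 2 h; one pre-dose timepoint; four readings (protocol) or five (SAP); 10 completers.

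**Assumed.** The within-day CV of the FEV1 value used at each timepoint is not in the documents, so a range is shown. The ±20% rule on pre-dose FEV1 at Visits 3 and 4 is a between-visit limit and does not supply it. The base case has independent log-normal errors, including at baseline, and no drift.

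**Formula.** With s = √ln(1 + CV²), log errors e₀ at baseline and e₁…e_k after dosing, a null profile shows onset if max(e_j − e₀) ≥ ln 1.10 = 0.0953. For one reading the chance is 1 − Φ(0.0953 / (s√2)). At CV 5%, s = 0.0500, s√2 = 0.0707, z = 1.349, so the chance is 8.9%. Four independent chances would give 1 − (1 − 0.089)⁴ ≈ 31%. The readings share one baseline, so the joint figure is lower and was simulated (400,000 profiles per scenario).

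| CV | One reading | Four readings | Five readings | Expected among 10 null profiles (four / five) |
|---|---|---|---|---|
| 2% | <0.1% | 0.1% | 0.2% | 0.0 / 0.0 |
| 3% | 1.3% | 4.1% | 4.9% | 0.4 / 0.5 |
| 4% | 4.5% | 13.4% | 15.5% | 1.3 / 1.5 |
| 5% | 8.9% | 23.4% | 26.5% | 2.3 / 2.7 |
| 6% | 13.1% | 32.1% | 35.9% | 3.2 / 3.6 |
| 8% | 19.9% | 44.4% | 48.7% | 4.4 / 4.9 |
| 10% | 24.9% | 52.1% | 56.5% | 5.2 / 5.7 |

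**Sensitivity, four readings.**
- Correlation 0.5 between all readings: 0.3%, 9% and 29% at CV 3%, 5% and 8%.
- Assumed upward drift reaching 4% at 2 h, independent errors: 13%, 35% and 52% at the same CVs.

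**When noise alone gives a median.** All censoring is at 2 h, so a Kaplan-Meier median exists only if at least half the profiles cross. Under the null that needs a CV of about 9.4% (four readings) or 8.3% (five).

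**With a real effect (four readings, CV 5%).** A flat true rise of 5%, which never reaches the threshold, gives cumulative onset of 26%, 39%, 47% and 53% at 15 min, 30 min, 1 h and 2 h. A median of 2 h would then be reported. A flat true rise of 14%, the maximal mean increase quoted for asthma in Protocol 1.1, gives 92% by 2 h against the 23% null rate.

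**Clock origin.** The SAP leaves it as start/end of nebulisation. Protocol 5.4.2 sets Time 0 at the end and limits nebulisation to 10 minutes. A crossing at the 15-minute reading is therefore 15 minutes on one clock and up to 15 + 10 = 25 on the other.

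**The case against.** The best defence is that placebo is not excluded. The word in brackets qualifies only the median, and the sentence on the plot leaves out no arm. There is also a sensible reason to give the median for active groups only: unless at least half of placebo profiles cross, placebo has no Kaplan-Meier median, and in the base case that takes a CV above about 8%. This stands. A reader might infer that placebo is kept off the plot. The text supports only that its inclusion is not stated.

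The background is also partly visible elsewhere. Spirometry is summarised by treatment and timepoint with change from baseline, individual curves are planned, and the timepoint tests against placebo would show early separation if early timepoints are included. A reader could count placebo crossings from Listing 16.2.6.1. The general table of pharmacodynamic parameters (14.2.2.2) might carry onset, though the SAP does not say so. This too stands. A reader might conclude that bronchodilation cannot be attributed to RPL554, and the documents do not support that, because peak, average and timepoint effects are all compared with placebo.

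Finally, the primary endpoint is pharmacokinetic. Onset is absent from the secondary objectives, is untested, and rests on about 10 patients in a convenience sample. That limits the weight of the point. None of these arguments supplies the direct placebo onset figure.

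**Conclusion.** The point holds for the onset summary taken alone. As specified, it has a threshold with no placebo correction or confirmation, an unnamed reference, a median for active groups only, no placebo contrast and no listed output. It cannot by itself show how much of the observed onset is background.

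The size of the problem is unknown. A reader might infer that ordinary spirometry noise will give onset in many placebo profiles. That depends on a CV the documents do not provide: the null rate is near zero at 2%, about 4-5% at 3%, 23-27% at 5% and 32-36% at 6% with independent errors and no drift, and 9% at 5% with four readings and correlation 0.5. Any drift is likewise an assumption. Because the rate cannot be settled from the documents, the trial's own placebo profiles should supply it. A large effect would still stand out. The summary is most open to misreading when the true effect lies below the threshold, as in the 5% example.

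**What to change.** In SAP 6.4.6.1:
- name the day's pre-dose FEV1 as the reference for the 10% rise;
- derive onset for placebo exactly as for the two doses;
- show all three treatments on the Kaplan-Meier plot;
- report n (%) reaching 10% by 2 h for each treatment;
- state that active medians will be interpreted against the placebo curve.

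Add the figure and the table to SAP 8. Reconcile the start/end clock origin with Time 0 in Protocol 5.4.2, and the 5-minute reading in SAP 4.4.1 with the schedule in Protocol 7.2.1.

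The cost is a few lines of text and two outputs, using the spirometry already planned. The apparent onset rate attributable to drug may look less favourable. Requiring two consecutive readings would cut the four-reading null rate at CV 5% from 23% to 6%, but it changes the endpoint. The placebo curve addresses the problem without doing so.
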